**ABBREVIATIONS**

AE	adverse event
CEC	Clinical Endpoint Committee
CI	confidence interval
CRF	case report form
CSR	Clinical Study Report
DMC	Data Monitoring Committee
DPS	Data Presentation Specifications
IDMC	Independent Data Monitoring Committee
eCRF	electronic case report form
ELISA	Enzyme-linked immunosorbent assay
ELISpot	enzyme-linked immunospot
GMC	Geometric mean antibody concentration
FA	Full Analysis Set
FDA	Food and Drug Administration
ICH	International Conference on Harmonization
ITT	Intent-to-Treat
ICS	Intracellular Cytokine Staining
IU/ml	International units per milliliter
IVRS	interactive voice response system
LLOQ	lower limit of quantification
LOCF	last observation carried forward
LRTI	lower respiratory tract infection
MedDRA	Medical Dictionary for Regulatory Activities
NA	Not Applicable
PI	principal investigator
PPI	Per-protocol Immunogenicity
RSV	Respiratory syncytial virus
RTI	Respiratory tract infection
SAE	serious adverse event
SAP	Statistical Analysis Plan
SD	standard deviation
TLF	Tables, Listings and Figures

**DEFINITION OF TERMS**

Active vaccine	Ad26.RSV.preF
Study vaccine	Ad26.RSV.preF or Placebo

## 1. INTRODUCTION

This is the Statistical Analysis Plan (SAP) applicable for the VAC18194RSV2001 trial. This SAP is applicable for the following analysis:

- **Cohort 0:** primary analysis will be performed when all subjects have reached Day 57 (28 days post-Dose 2) or discontinued earlier. All available safety and immunogenicity data gathered so far will be included in the analysis; unblinded at the group level.
- **Cohort 1:** interim analysis will be performed when 12 subjects have reached Day 8 or discontinued earlier. All available safety of the 12 subjects and all available immunogenicity data gathered up to that point will be included in the analysis; unblinded at the group level. For the safety analysis snapshot data will be used: there will be no formal cleaning for this analysis. Data will be cleaned in an ongoing basis.
- **Cohort 1:** interim analysis will be performed when at least 12 subjects have reached Day 29 or discontinued earlier. All available safety and all immunogenicity data gathered up to that point will be included in the analysis; unblinded at the group level.
- **Cohort 1:** Depending on the outcome of the first 2 interim analysis of Cohort 1 an additional interim analysis may be performed when at least 24 subjects have reached Day 29 (28 days post-Dose 1) or discontinued earlier. All available safety and immunogenicity data gathered so far will be included in the analysis; unblinded at the group level.
- **Cohort 1:** primary analysis will be performed when all subjects have reached Day 57 (28 days post-Dose 2) or discontinued earlier. All available safety and immunogenicity data gathered so far will be included in the analysis; unblinded at the group level.
- **Final analysis of both cohorts;** at the end of the study, 1 year after the first dose; unblinded.
- Additional interim analyses (blinded or unblinded at the group level) may be performed during the study for the purpose of informing future vaccine-related decisions in a timely manner, or upon health authority request.

This document contains all information needed for performing a full safety and immunogenicity analysis. Tables, listings and figures (TLF) which need to be generated for each analysis will be described in separate data presentation specifications (DPS) document.

## 1.1. Trial Objectives

### *Primary Objective*

- To assess the safety and tolerability of an intramuscular regimen of two doses of  $1 \times 10^{11}$  viral particles (vp) of Ad26.RSV.preF in adults aged 18 to 50 years.
- To assess the safety and tolerability of an intramuscular regimen of two doses of  $5 \times 10^{10}$  vp of Ad26.RSV.preF in RSV-seropositive toddlers aged 12 to 24 months.

### *Secondary Objectives*

- To assess the humoral and cellular immune responses as measured by virus neutralization assay, F-protein binding antibodies (pre-F and post-F) and intracellular cytokine staining (ICS; to assess Th1/Th2 subtyping).

### *Exploratory Objectives*

- To further assess the humoral and cellular immune responses elicited by Ad26.RSV.preF. The assays to be used may include, but are not limited to, RSV strain cross-neutralization, anti-F protein antibody specificity and functionality characterization, adenovirus neutralization assays, molecular antibody characterization (avidity, Fc cell interaction, antibody isotyping), evaluation of the cellular immune response (interferon gamma [IFN $\gamma$ ] enzyme-linked immunospot [ELISpot] assay) and functional and memory immune response (by ICS), and cytokine profiles of RSV F-protein peptide-stimulated peripheral blood mononuclear cell (PBMC) supernatant.
- To assess RSV infection rates in Ad26.RSV.preF and placebo subjects.
- To monitor for severe RSV-lower respiratory tract infection (LRTI) in Cohort 1 (RSV-seropositive toddlers aged 12 to 24 months).
- To assess symptoms of respiratory illness via the respiratory tract infection (RTI) symptoms

## 1.2. Trial Design

This is a multi-center, randomized, double-blind, Phase 1/2a study, to be conducted in 12 male and female adults aged  $\geq 18$  to  $\leq 50$  years and 36 male and female RSV-seropositive toddlers aged  $\geq 12$  to  $\leq 24$  months of age.

Subjects will be enrolled into sequential age cohorts:

- 18 to 50-year-old adults, into **Cohort 0**
- 12 to 24-month-old seropositive toddlers, into **Cohort 1**

In Cohort 0, subjects will be randomized 2:1 to receive either Ad26/Ad26 ( $1 \times 10^{11}$  vp in 0.5 mL) or placebo/placebo (saline), and in Cohort 1, subjects will be randomized 2:1 to receive either Ad26/Ad26 ( $5 \times 10^{10}$  vp in 0.25 mL) or placebo/placebo. A schematic overview of the study design and groups is depicted in [Table 1](#).

**Table 1: Study Design**

Cohort	Group	N	Day 1	Day 29/Week 4
ADULTS 18 to 50 years				
0	Group 1	8	Ad26.RSV.preF (1x10  vp)	Ad26.RSV.preF (1x10  vp)
	Group 2	4	Placebo	Placebo
TODDLERS 12 to 24 months: RSV seropositive				
1	Group 3	32	Ad26.RSV.preF (5x10  vp)	Ad26.RSV.preF (5x10  vp)
	Group 4	16	Placebo	Placebo

The study will have three phases: a **screening phase**, an **active phase** and a **safety follow-up phase** through 1 year after the first dose.

The end of the active phase will be when the last subject completes the visit at 6 months after the final

dose. The end of the study will be the last subject's last visit (by telephone) at the end of the safety follow-up phase. For further information related to the design of the study refer to CTP, Section 3.1.

### 1.3. Statistical Hypotheses for Trial Objectives

The objective of the study is to evaluate whether Ad26.RSV.preF is safe, well-tolerated and immunogenic in adults and RSV-seropositive toddlers. No formal statistical hypothesis is planned. Safety parameters will be summarized descriptively. Geometric mean titers with 95% confidence intervals (CI) for humoral assays and medians with interquartile for cellular assays will be calculated.

### 1.4. Sample Size Justification

The number of subjects chosen for this study will provide a preliminary safety and immunogenicity assessment. Placebo recipients are included for blinding and safety purposes and will provide additional control specimens for immunogenicity assays.

### 1.5. Randomization and Blinding

Central randomization will be implemented in this study. Within each cohort, subjects will be randomly assigned to one of the two groups based on a computer-generated randomization schedule prepared before the study by or under the supervision of the sponsor. The randomization will be balanced by using randomly permuted blocks. No stratification will be applied. The interactive web response system (IWRS) will assign a unique code, which will dictate the group assignment for the subject. The requestor must use his or her own user identification and personal identification number when contacting the IWRS, and will then give the relevant subject details to uniquely identify the subject.

The subjects, study-site personnel, and investigator will be blinded to study vaccine allocation throughout the study, except for the pharmacist or qualified staff member with primary responsibility for study vaccine preparation and dispensing. Unblinding will occur at the time of

the first interim analysis. The results will only be available to a selected group of sponsor personnel, excluding personnel involved in data collection and data management. For further information please refer to CTP Section 5.

## **1.6. Changes to planned analyses**

Two addition interim analyses for Cohort 1 have been added, for the purpose of informing future vaccine-related decisions in a timely manner. The first interim analysis will be performed when 12 subjects have reached Day 8, and the second one when at least 12 subjects have reached Day 29. Given that the first interim analysis coincides with the planned IDMC analysis, the IDMC members will receive immediately unblinded at the group level safety results instead of blinded, as specified in the CTP. That way the IDMC and the study team will possess the same information regarding safety. Moreover, the conduct of the planned interim analysis, when at least 24 subjects of Cohort 1 have reached Day 29 (28 days post-Dose 1) or discontinued earlier, will be dependent on the outcome of the previous interim analyses and is at the discretion of the sponsor.

## **2. GENERAL ANALYSIS DEFINITIONS**

### **2.1. Study phases**

A baseline (or reference) value will be defined as the value of the last available assessment prior to the first vaccination on Day 1.

The safety analysis will present all results by period. Immunogenicity results will be presented per scheduled time point as appropriate. Listings will be shown per phase and time point.

Study day or relative day is defined as follows:

Study Day = visit date - date of Day 1 + 1; if visit date > date of Day 1 (date of first vaccination).

Study Day = visit date - date of Day 1; if visit date < date of Day 1 (date of first vaccination).

### 2.1.1. Phase definitions

The phases in the study will be constructed as follows:

**Table 2: Phase Definitions**

Phase	Phase #	Period	Period #	Interval	
				From	To
Screening	1			Date and time of signing the informed consent form a	One minute prior to start of post dose 1 period
Regimen	2	Post-dose 1	1	Date and time of first vaccination (Visit Day 1)	Minimum of: 
 
a) One minute prior to date and time of the next vaccination. If second vaccination was not administered then use maximum (28 days after first vaccination at 23:59, scheduled visit 4 weeks after first vaccination at 23:59)
 
b) 23:59 at the date of last contact (for early discontinuation)
 
c) 23:59 at the date of database cut-off ate in case of interim.
 

Regimen	2	Post-dose 2	2	Date and time of second vaccination (Visit Day 29)	Minimum of: 
 
a) Maximum (28 days after second vaccination at 23:59, scheduled visit 4 weeks after second vaccination at 23:59)
 
a) 23:59 at the date of last contact (for early discontinuation)
 
b) 23:59 at the date of database cut-off date in case of interim.
 

Follow-up	3			One minute after the last Post-dose period ends	
 
a) 23:59 at the date of last contact.
 
b) 23:59 at the date of database cut-off date in case of interim.
 

a in case an earlier date is available (eg. for lab or vital signs), then use the very first date to include all data

## 2.2. Pooling Algorithm for Analysis Centers

Data will be pooled across the different centers.

## 2.3. Analysis Sets

### 2.3.1. Full Analysis Set (FA)

The **Full Analysis (FA) Set** includes all subjects who were randomized and received at least one dose of study vaccine, regardless of the occurrence of protocol deviations. Vaccination assignment will follow the as-treated principle. All safety analyses will be based on the FA set. As a sensitivity analysis, key immunogenicity tables will also be based on the FA set.

### 2.3.2. Immunogenicity Analysis Set

#### 2.3.2.1. Per Protocol Immunogenicity Population (PPI)

The **Per-protocol Immunogenicity Set (PPI)** will include all randomized and vaccinated subjects for whom immunogenicity data are available, excluding subject samples with major protocol deviations expecting to impact the immunogenicity outcomes.

In addition, the following samples will not be included in the PPI set:

- If subjects miss one or more doses, but continue the planned visit schedule, samples taken after the planned but missed dose(s) will not be taken into account;
- For subjects who experience a natural RSV infection (based on RT-PCR, or other sources), samples taken after the natural infection are not be taken into account.

The analysis of immunogenicity will be based on the PPI set.

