**TIME AND EVENTS SCHEDULE – COHORT 1: SEROPOSITIVE TODDLERS**

Phase	Screening	Active									Safety FU a
Clinic Visit #	1	2	3	4	5	6	7	8	9 b	Exit d	During both the active and safety FU phases: FU outside RSV season at 30-day intervals; FU in season at 14-day intervals
Visit Timing		Vac 1	Vac 1 + 3 d	Vac 1 + 7 d	Vac 2	Vac 2 + 3 d	Vac 2 + 7 d	Vac 2 + 28 d	Vac 2 + 6 mo		
Visit Week		0		1	4		5	8	30		
Target Visit Day ±window	-42 to 1	1	4±1 f	8±2 g	29±3	32±1 f	36±2	57±3	211±14		
Visit Type	Screening	VACCINE 1	Safety (Telephone)	Safety	VACCINE 2	Safety (Telephone)	Safety	Safety and Immuno.	Safety and Immuno.	Early Exit	Safety FU (Telephone)
Written informed consent h	●										
Inclusion/exclusion criteria	●										
Demographics	●										
Medical history/pre-study meds	●										
Body height and weight	●	①			①			●	●	●	
Physical examination	●	①②		②	①②		②	②	②	②	
Vital signs j incl. body temperature	●	⑥		●	⑥		●	⑩	⑩	⑥	
RSV serostatus testing l,m	●	0.5 mL									
Randomization		①									
Inclusion/exclusion criteria check o		①			①						
Prevaccination symptoms q		①			①						
Cellular immunity		④ 4 mL			④ 4 mL					④ 4 mL	
Humoral immunity p		④ 1 mL			④ 1 mL			● 2 mL	● 2 mL	④ 1 mL	
Vaccination w		●			●						
30 minute or 60 minute post-vaccination observation r		●			●						
Solicited AE recording		----- Continuous -----			----- Continuous -----						⑥
Unsolicited AE recording		----- Continuous -----									⑦
SAE recording		----- All SAEs -----									●
Concomitant meds s		----- Continuous -----									●
RTIs t		----- Continuous -----									
RTI Symptoms Form u		----- Continuous -----									
Severe LRTIs; MA-RTIs		----- Continuous -----									

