- For those subjects who are unable to continue participation in the study up to Visit 9, but for whom consent is not withdrawn, an exit visit will be conducted as soon as possible
- On Days 3 and 31, a telephone call will *additionally* be made to sentinel subjects in Cohort 0 to collect safety information
- On Days 3 and 31, a telephone call will *additionally* be made to parent(s)/legal guardian(s) of sentinel subjects in Cohort 1 to collect safety information
- If any subject in Cohort 0, or any of the first 12 subjects in Cohort 1 come in earlier than Day 8 for Visit 4 (allowed window is ±2 days), a subsequent phone call will be made at the end of the diary period to collect diary card information recorded between the actual visit and the end of the diary period on Day 8
- Signing of the ICF should be done before any study-related activity
- Systolic and diastolic blood pressure, respiratory rate, heart rate, body temperature
- Respiratory rate, heart rate, body temperature
- For women of childbearing potential only

- l. 0.5 mL of blood for serostatus assessment can be collected at screening by venous blood sample or fingerstick, at the discretion of the investigator. If 0.5 mL is collected at screening, baseline blood draw for immunogenicity should be on Day 1.
- m. Note: RSV-seropositive toddlers may be recruited if RSV seropositivity was assessed via RSV EIA or virus neutralization assay in a different study of the sponsor.
- n. Cohort 0: to include exclusion criteria 1, 4, 8, 9, 10, 11, 15, 16 and 17
- o. Cohort 1: to include exclusion criteria 21, 22, 25, 26, 28, and 32
- p. Blood for cellular immunity will also provide plasma for humoral assessments
- q. Investigator must check for acute illness or body temperature  $\geq 38.0$  °C at the time of vaccination. If before the first vaccination, the subject may be enrolled at a later date if within the screening window (otherwise, rescreening is required), or be withdrawn at the discretion of the investigator and after consultation with the sponsor. If before the second vaccination, the subject may be vaccinated up to, and no later than 10 days after the scheduled vaccination, or be withdrawn at the discretion of the investigator and after consultation with the sponsor. In the event of an ongoing AE or other situation precluding subject vaccination within 10 days, subjects may be vaccinated beyond the 10-day window at the discretion of the sponsor.

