### **9.1.2. Visit Windows**

For the following visits, windows will be allowed as indicated:

- Second vaccination:  $\pm 3$  days (both cohorts)
- 3 days post-vaccination safety only visit:  $\pm 1$  day
- 7 days post-vaccination safety only visit:  $\pm 2$  days
- 28 days post-final vaccination safety and immunogenicity visit:  $\pm 3$  days
- 6 months post-final vaccination safety and immunogenicity visit:  $\pm 14$  days
- 1 year post-first vaccination safety follow-up telephone call:  $\pm 14$  days

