### 11.1. Analysis Sets

The **Full Analysis Set (FA)** includes all subjects who were randomized and received at least one dose of study vaccine, regardless of the occurrence of protocol deviations. Vaccination assignment will follow the as-treated principle. All safety analyses will be based on the FA set. As a sensitivity analysis, key immunogenicity tables will also be based on the FA set.

The **Per-protocol Immunogenicity Set (PPI)** will include all randomized and vaccinated subjects for whom immunogenicity data are available, excluding subjects with major protocol deviations expected to impact the immunogenicity outcomes.

In addition, the following samples will not be included in the PPI set:

- If subjects miss one or more doses, but continue the planned visit schedule, samples taken after the planned but missed dose(s) will not be taken into account;
- For subjects who experience a natural RSV infection (based on RT-PCR, or other sources), samples taken after the natural infection are not be taken into account.
- Any subject who receives study vaccine beyond the Day 29 window specified in the Time and Events Schedule would not be included in the per-protocol immunogenicity analyses.

The analysis of immunogenicity will be based on the PPI set.

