#### **11.5. Immunogenicity Analyses**

No formal hypothesis on immunogenicity will be tested. Descriptive statistics (geometric mean and 95% confidence interval [CI] for ELISA and virus neutralization assays; median and quartiles for ELISpot and ICS) will be calculated for continuous immunologic parameters at all timepoints. Graphical representations of immunologic parameters will be made as applicable.

Frequency tabulations will be calculated for discrete (qualitative) immunologic parameters as applicable.

The primary analysis set for immunogenicity is the PPI set. As a sensitivity analysis, key tables will also be based on the FA set. Depending on their occurrence, the effect of missed doses or natural infections might be further explored. Note that they will be included in the tables showing the FA set.

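### SAP 2.3.2.1 leaves out the protocol's exclusion of late-vaccinated subjects from the Per-protocol Immunogenicity set and words the deviation clause by sample

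*SAP*

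**What the plan says.** Protocol 11.1 builds the Per-protocol Immunogenicity (PPI) set from randomized, vaccinated subjects with immunogenicity data, "excluding subjects with major protocol deviations expected to impact the immunogenicity outcomes". It then lists three further exclusions: samples after a missed dose, samples after a natural RSV infection, and a third rule: "Any subject who receives study vaccine beyond the Day 29 window specified in the Time and Events Schedule would not be included". The amendment history shows that the third rule came in with Amendment 3. Protocol 11.5 fixes the status of the set: "The primary analysis set for immunogenicity is the PPI set".

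SAP 2.3.2.1 starts from the same population, "excluding subject samples with major protocol deviations expecting to impact the immunogenicity outcomes", lists the first two further exclusions, and stops. No other SAP section restores the third.

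SAP 1.6, the section for changes to planned analyses, opens with "Two addition interim analyses for Cohort 1 have been added". It goes on to the IDMC receiving group-level unblinded safety results and to the interim analysis at 24 toddlers becoming conditional. It does not mention the PPI set.

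**The concern.** SAP 1 says that the document is sufficient for the full safety and immunogenicity analysis, and its scope includes the primary analysis of each cohort and the final analysis. Someone programming the PPI flag from it would find no rule on late vaccination.

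If a second dose is late, that subject stays in the set on which immunogenicity is primarily reported, against the protocol. The wording by sample adds a second uncertainty. Even if a late dose were treated as a major deviation, the SAP does not say whether the whole subject goes or only some of the samples.

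**Working it through.** The documents state no figure for this point, so the check is a comparison of clauses followed by simple shares.

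**1. Clauses side by side**

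| Element of the PPI definition | Protocol 11.1 | SAP 2.3.2.1 |
|---|---|---|
| Major deviations | removes subjects | removes subject samples |
| Missed dose | later samples removed | same |
| Natural RSV infection | later samples removed | same |
| Vaccination beyond the Day 29 window | subject removed | absent |

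Additional exclusions listed: 3 in the protocol, 2 in the SAP.

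**2. Does the general deviation clause fill the gap?** Not reliably. Footnote q of the Time and Events Schedule covers illness or fever at the second visit: "If before the second vaccination, the subject may be vaccinated up to, and no later than 10 days after the scheduled vaccination". The same footnote, and protocol 9.1.4.2.1 and 10.3, let the sponsor allow vaccination later still when an ongoing adverse event or another obstacle rules out those 10 days. A late dose can therefore comply with the protocol. SAP 4.4 says only that major deviations are summarized.

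**3. Which window?** The schedule row "Target Visit Day ±window" gives 29±3 for the second vaccination, and protocol 9.1.2 gives the same ±3 days. That is Day 26 to Day 32 (29 − 3 and 29 + 3). Counted from Day 29, the 10-day allowance reaches Day 39 (29 + 10). The natural reading of the exclusion is 29±3. However, footnote q sits in the same schedule, so a dose on Days 33 to 39 could be argued either way until the rule names its window.

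**4. By subject or by sample.** Protocol 3.1 schedules humoral sampling before each dose and at 28 days and 6 months after dose 2. In Cohort 1, scheduled cellular sampling occurs only before dose 1 and before dose 2, and an early exit after Day 29 collects humoral blood only. So every scheduled Cohort 1 cellular sample precedes dose 2. A by-subject rule removes all of a late-dosed toddler's samples. Under a by-sample rule, the samples drawn before the late dose, including all scheduled cellular ones, may stay in.

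**5. Size.** The documents give no rate of late second doses. One late subject is:

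- Cohort 1 active: 1/24 = 4.2%
- Cohort 1 placebo: 1/12 = 8.3%

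**6. Group sizes in the SAP.** SAP Table 1 has 32 + 16 = 48 toddlers. SAP 1.2 says 36, and protocol Table 5 has 24 + 12 = 36.

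**7. Sensitivity tables.** SAP 2.3.1 and protocol 11.1 and 11.5 commit to key immunogenicity tables on the Full Analysis set. SAP 6 says only that the most important tables *might* be repeated on it.

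**The case against.** The strongest answer is version lag. The late-dose rule arrived with Amendment 3. The 48 toddlers in SAP Table 1 match the protocol after Amendment 2 and before Amendment 4. SAP 1 and 1.6 treat the 24-toddler interim analysis as conditional and still ahead, whereas the Amendment 4 entry reports that the IDMC has already reviewed it. The 36 in SAP 1.2 does not settle the date, because 36 was also the size before Amendment 2 added 12 (48 − 12 = 36). This is inference, since the SAP's date is not visible, but it is plausible. It explains the omission without removing the conflict with the current protocol.

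It is also true that the general clause could still catch a late dose judged to be a major deviation, that no hypothesis is tested, and that Full Analysis tables would give a second view.

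Some stronger readings are tempting but not supported:

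- *The SAP loosened the set without declaring it.* If the SAP predates Amendment 3, SAP 1.6 had no late-dose departure to declare. Its silence is secondary.
- *The wording by sample is plainly a SAP departure.* The protocol is itself mixed. Its subject-level late-dose rule stands under a lead-in about samples, and the other two rules work by sample.
- *A by-sample rule would remove a known number of samples.* The SAP does not say which samples a late dose affects. If the whole second visit slips, the pre-dose samples drawn there may also be off schedule.
- *The harm is wider confidence intervals.* Lost precision is the cost of applying the exclusion. Omitting it risks a shift in titers or fold increases, and the documents give no basis for estimating that.
- *Late doses would go unreported.* SAP 4.3 counts only missed vaccinations, but the outputs are specified in separate documents that are not available here.

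**Conclusion.** The point holds as a conflict between a stated protocol rule and the SAP text. It should be corrected, but it is modest in weight. As written, the SAP can place protocol-excluded subjects in the primary immunogenicity set.

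The effect is nil if no second dose is late. Otherwise each late subject is one of the 24 active or 12 placebo toddlers, on secondary, descriptive endpoints. The conclusion assumes that the SAP supplied is the one governing the primary and final analyses, and that a permitted late dose is not automatically classed as a major deviation. It does not depend on why the rule is missing.

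**What to change.** 1. Add the protocol 11.1 late-vaccination exclusion to SAP 2.3.2.1, or declare and justify the departure in SAP 1.6.
2. In that bullet, name the schedule window that decides membership of the set (29±3 in the schedule row and in protocol 9.1.2). This defines the analysis set only and leaves every dosing allowance as it stands. State that the exclusion acts by subject, as the protocol bullet does, and reconcile this with the lead-in about samples in protocol 11.1. This settles whether pre-dose 2 samples, including all scheduled Cohort 1 cellular samples, stay in.
3. Correct SAP Table 1 to 24 + 12.
4. In SAP 6, change *might* to *will* for the Full Analysis sensitivity tables, to match SAP 2.3.1 and protocol 11.1 and 11.5.

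The cost is wording, with no new data. The downside is that the PPI set may be slightly smaller than under the present SAP text.
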